## **SECTION 5 METHODS: DATA COLLECTION, MANAGEMENT, AND ANALYSIS**

### **SECTION 5.1 Data collection methods**

#### **5.1a Outcomes and time points at which they will be assessed**

Outcome	Measurement	Time point
Demographics	Age, sex, height, weight, affected knee, mechanism of injury (traumatic/atraumatic), previous history of ipsilateral patella dislocation, previous history of contralateral patella dislocation,	Baseline

	time from injury to presentation to acute care (ED or trauma services), family history of patella dislocation, employment status, level of education, ethnicity	
Assessment findings	
Presence/absence of the following on:
 
 
• A convincing patient history of a visible deformity on the lateral aspect of the knee or a sensation of the patella ‘popping’ out of joint followed by spontaneous reduction
 
• Presence of a haemarthrosis or joint effusion on clinical examination
 
• Tenderness along the medial patellofemoral complex (tenderness at the following bony landmarks or at any point extending between these two points: at or just proximal to the medial epicondyle of the femur and the midpoint of the medial aspect of the patella extending to the junction of the medial quadriceps tendon and the patella)
 
• Apprehension on laterally directed force of the patella
 
	Baseline
Eligibility	% of participants with a diagnosis of LPD who meet the eligibility criteria	Completion of study
Recruitment	
% of eligible participants who consent to participate in the study
 
Reasons for not consenting will also attempt to be collected
	Completion of study
Adherence	% of scheduled physiotherapy sessions attended	
Completion of intervention
 
3 months post first

	Participant self-reported % of prescribed home exercise sessions completed	physiotherapy session
Acceptability	% attrition rate  Patient satisfaction questionnaire	Completion of study  3 months post first physiotherapy session
Follow up	% of participants who consent to treatment who return 3 month questionnaires	Completion of study
Knee function, pain and instability	Lysholm Knee Scoring Scale	Baseline, 3 months post first physiotherapy session
Activity level	Tegner Activity Scale	Baseline, 3 months post first physiotherapy session
General health status	EQ-5D-5L	Baseline, 3 months post first physiotherapy session
Intervention delivery	Duration from LPD to first physio session, initial injury management, number of physiotherapy sessions attended, number of physiotherapy appointments participants unable to attend/did not attend, duration of the intervention from enrolment to discharge, exercises and dose of exercise	Completion of intervention

	prescribed from treatment logs completed by therapists	
Harms	Patient and staff reported adverse events including any recurrent patellar dislocation, subsequent listing for knee surgery for mechanical instability and any increases in pain or swelling resulting from the exercise intervention lasting > 1 week	From beginning of intervention to 3 months post first physiotherapy session

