### **3.2b Secondary objectives**

- To determine the acceptability of outcome data collection to participants by measuring the completion rates of PROMs
- Assess harms associated with participation in the study
- To determine what assessment findings are consistent with a diagnosis of LPD.
- Assess delivery of the intervention

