#### **4.2a Inclusion and exclusion criteria**

Inclusion criteria:

- Male or female  $\geq 16$  years of age
- Attending the John Radcliffe trauma and orthopaedic service NPC or referred to the trauma outpatient physiotherapy department
- First time or recurrent LPD (traumatic or atraumatic) meeting the diagnostic criteria of 1) requiring reduction by paramedics **or** 2) diagnosed by a member of the trauma and orthopaedic team.

Exclusion criteria:

- Concurrent anterior cruciate ligament or posterior cruciate ligament injury confirmed by negative Lachman's and posterior drawer test or confirmed by Magnetic Resonance Imagery (MRI); medial collateral and lateral collateral ligament injury requiring application of a hinged knee brace or surgical repair; concomitant injury that would prohibit participation in the exercise intervention
- > 4 weeks from injury to presentation to acute care (ED or trauma services)
- Unable to give written informed consent
- Previous surgery on the affected knee
- Presence of fracture on plain radiograph including osteochondral fractures
- Medial patellar dislocation
- Considered inappropriate for referral to physiotherapy (by member of trauma and orthopaedic team assessing the patient)
- History of severe neuromuscular or congenital disorders
- Patients referred for orthopaedic opinion who are subsequently listed for surgery prior to completion of the study intervention
- Unable to understand written or spoken English
- Unable to attend physiotherapy sessions at the John Radcliffe trauma outpatient physiotherapy department

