- Harms. For this study harms will be defined as any unfavourable sign or symptom related to completing the study intervention. The recording of harms has been recommended in feasibility studies to inform future research design and processes. This will be measured from commencement of the intervention to 3 month follow-up as outlined in section 6.2a.
- Determine what assessment findings are consistent with a diagnosis of LPD. A member of the trauma and orthopaedic team will be required to assess the presence/absence of proposed assessment findings to include in the eligibility criteria for future studies as outlined in section 5.1. This will inform the feasibility of using these assessment findings in the eligibility criteria for future studies.

- Intervention delivery. Treatment logs will be analysed to record the duration from injury to commencing the intervention, the number of physiotherapy sessions received by participants, the duration of intervention and the exercises prescribed.

Additional demographic data will be collected as part of the study. Further information on this and the time points for data collection are outlined in section 5.1

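### The history item among the baseline assessment findings mixes symptom history with mode of reduction, and has no scoring rule for patients whose patella was reduced by someone else

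*Combined protocol and SAP*

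**What the plan says.** Section 3.2b sets a secondary objective: "To determine what assessment findings are consistent with a diagnosis of LPD". Section 4.4b has a member of the trauma and orthopaedic team "assess the presence/absence of proposed assessment findings to include in the eligibility criteria for future studies", and adds: "This will inform the feasibility of using these assessment findings in the eligibility criteria for future studies".

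The findings are listed in the outcomes table of Section 5.1a. The first is a history item with two limbs joined by 'or'. It opens "A convincing patient history of a visible deformity on the lateral aspect of the knee or a sensation of the patella", then refers to popping, and closes "out of joint followed by spontaneous reduction".

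Section 4.2a gives two alternative diagnostic routes into the study. The first is "meeting the diagnostic criteria of 1) requiring reduction by paramedics"; the second is being "diagnosed by a member of the trauma and orthopaedic team". Neither route requires the patella to have gone back by itself, and the first describes a patella that did not.

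The demographics row of Section 5.1a does not include mode of reduction. The intervention-delivery row takes initial management of the injury from the therapists' treatment logs, but does not name mode of reduction as a field. Section 5.3a plans counts and percentages for categorical data, with no breakdown or special denominator for this item.

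**The concern.** The item asks two things in one tick-box: whether the patient describes a dislocation, and whether it reduced spontaneously. A patient whose patella stayed out until someone else put it back may answer yes to the first and no to the second. The protocol does not say which answer goes on the form, nor does it take such patients out of the denominator.

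At stake is how the item's frequency is read. A low count could mean that patients with a lateral patellar dislocation seldom give this history, or that some gave it and were marked absent because of how the knee was reduced. Counts and percentages alone cannot separate the two. The patients affected are ones whom the protocol itself accepts as having the diagnosis. If the item were carried unchanged into future eligibility criteria, the same ambiguity would go with it. Section 4.1 names both physiotherapists and orthopaedic surgeons as clinic assessors of eligibility. If the findings are scored by a similar mix of staff, two assessors could resolve the wording differently.

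**Working it through.** The protocol states no expected frequency for this item and has no power calculation, so there is no planned figure to reproduce. The check is of the item's wording against the entry criteria, followed by a range for the possible effect.

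**Inputs**
- N = 15, the recruitment target (Section 4.6a).
- f = share of participants whose patella was reduced by someone else. Not in the documents; assumed 10%, 25% or 40%.
- p = share of the other participants who meet the item. Not in the documents; set to 100% to find the ceiling that the wording alone imposes.
- d = share of assisted participants who report a visible lateral deformity. Not in the documents; assumed 100%, 80% or 50%.

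**Strict reading: the qualifier covers both limbs**

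No assisted participant can be scored present, so the frequency is (1 − f) × p. With p = 100%, in whole participants:
- f = 10%: 15 × 0.10 = 1.5, rounded to 2 absent; (15 − 2)/15 = 87%.
- f = 25%: 15 × 0.25 = 3.75, rounded to 4 absent; (15 − 4)/15 = 73%.
- f = 40%: 15 × 0.40 = 6 absent; (15 − 6)/15 = 60%.

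Without rounding to whole participants the ceilings are 90%, 75% and 60%.

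**Lenient reading: the qualifier covers only the popping limb**

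An assisted participant who reports a deformity is scored present, so the frequency is (1 − f) × p + f × d, and the shortfall from p is f × (p − d). With p = 100%:
- d = 100%: no loss at any f.
- d = 80%: loss = f × 0.2, giving 98%, 95% and 92% for f = 10%, 25% and 40%.
- d = 50%: loss = f × 0.5, giving 95%, 87.5% and 80%.

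**Is the case likely to arise in 15 participants?**

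The chance of at least one assisted participant is 1 − (1 − f)^15. At f = 10% it is 1 − 0.9^15 = 79%; at f = 20% it is 1 − 0.8^15 = 96.5%. Unless assisted reduction is rare here, some assessor will probably have to decide how to score it.

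**Set against sampling error**

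An observed 12 of 15 (80%) has an exact 95% confidence interval of 52% to 96%. A shift of one or two participants is small beside that. Unlike sampling error, though, a shift caused by the definition does not shrink in a larger study.

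**The case against.** A reader might infer that the item plainly requires spontaneous reduction, that clear-cut dislocations will therefore be scored absent, and that its frequency is biased low. The documents do not support this. The deformity limb is joined by 'or', and attaching the qualifier to the nearer limb is at least as natural: the first limb then describes a patella seen out of place, the second one that went back unaided. On that reading an assisted patient can meet the first limb, and the loss may be nil.

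A reader might also infer that these counts will decide which findings enter future criteria. Section 4.4b says only that they inform feasibility. No threshold, sensitivity estimate or decision rule is planned.

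Three further points deserve weight:
- **Intent.** The item may have been meant for patients without assisted reduction, as a complement to the first diagnostic route. The documents neither say so nor rule it out. If that is the intent, assisted patients belong outside the denominator, and mode of reduction must still be recorded to take them out.
- **Form instructions.** Section 5.2a promises staff written guidance on completing case report forms, which could hold a scoring rule. The protocol does not state one, and the guidance is not in the document.
- **Treatment logs.** Section 4.3 has acute care recorded there, and reduction might be noted. It is not a named field, and later recovery from records is uncertain: Section 3.1b reports that the team's own eligibility estimate was limited by what the medical records contained.

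So the objection removes any claim of demonstrated bias and the worst-case figures as a general result. It does not supply the missing rule.

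**Conclusion.** The point holds as an ambiguity with a conditional effect. As worded, the item can mark true dislocations absent: all assisted reductions on the strict reading, and those who felt popping but report no deformity on the lenient one. The ceilings of about 87%, 73% and 60% apply only to the strict reading and rest on assumed assisted shares of 10%, 25% and 40%. On the lenient reading the loss runs from zero to 20 percentage points over the ranges assumed above. The documents give neither the assisted share nor the share reporting deformity, so the actual size cannot be worked out from them.

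The reach is limited to one item of a descriptive secondary outcome. The primary outcomes and the target of 15 are unaffected. It is worth correcting because the remedy is small and serves the secondary objective under either reading, including the one in which the item was meant only for unassisted reductions.

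**What to change.** Before the first enrolment, replace the single history item on the baseline form with two:
- (a) history of a visible lateral deformity or of the patella popping out: present/absent, with no reference to how it reduced;
- (b) mode of reduction: spontaneous, by the patient, or by paramedic or hospital staff.

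In Section 5.3a, state that (a) will be reported as count and percentage in all participants and by category of (b). The frequency of the combined item, on whichever reading was intended, can then be approximated from (a) and (b). If the two readings must be told apart exactly, deformity and popping need separate boxes within (a).

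The cost is one reworded and one added tick-box. No treatment, entry criterion, primary outcome or sample size changes.

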To ensure progressive improvements in muscle strength, the prescribed dose of strengthening exercises will be in line with current guidelines. There is currently a lack of evidence to inform the most effective dose for exercises that incorporate sport specific and functional tasks such as agility, hopping and balance. Therefore, the dose of these exercises prescribed will be at the discretion of the physiotherapist and noted in the study treatment log. Patients will be required to perform the exercise programme independently a minimum of three times per week on non-consecutive days as recommended. Initially when pain may limit participants attaining the prescribed exercise intensity for strengthening exercise, participants can perform their exercises more frequently if they find this beneficial.

The intervention will also incorporate simple behaviour change techniques known to increase participant adherence to exercise. These will include goal setting, provision of written instruction, and demonstration and participant practice of the selected exercises.  
 Guidance and recommendations on how to implement these strategies into practice have been developed and have informed the design of our intervention.

At the initial assessment, participants will be required to select an activity related long-term goal. Short-term goals to be achieved by the next treatment session will be selected at all subsequent appointments except the last one. Participants will be facilitated in setting appropriate goals by their physiotherapist using recommended guidelines.

Written information will be provided in the form of a participant information booklet. This will contain information about the nature of their injury, self-management and guidance on the exercises to be completed. Rationale for the intervention and proposed benefits associated with this will be re-emphasised throughout the intervention.

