Physiotherapists will demonstrate the selected exercises followed by participants. Feedback will be provided, and participants will be asked if they would like to be recorded performing the exercises on their smartphone to increase technique compliance. The patient will be asked about their intention to adhere. If the intention is low, the barriers to adherence will be elicited and strategies to overcome them will be explored (following the principals of patient centred goal setting).

Participants will be provided with, and asked to complete, an exercise diary containing their exercises and guidance on achieving an effective dose. At the end of each session participants will be encouraged to ask questions, their understanding will be assessed and any clarifications needed will be provided. At each review session participant adherence and achievement of short-term goals will be reviewed and strategies to overcome any barriers will be explored

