### **SECTION 4.4 Outcomes**

#### **4.4a Primary outcomes**

- Eligibility defined as the % of participants with a diagnosis of LPD, screened for eligibility, who satisfy the eligibility criteria
- Recruitment rates defined as the % of eligible participants who consent to participate in the study
- Acceptability defined as the % attrition rate (participants who fail to complete follow up data collection at 3 months) and participant response to a patient satisfaction questionnaire
- Adherence defined as the % of scheduled physiotherapy sessions attended and participant self-reported intervention adherence defined as the % of prescribed exercise sessions completed

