### **5.3b Missing data**

Missing data for each questionnaire and item level missingness will be reported to help select future study outcome instruments.

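### Home-exercise adherence, part of a primary outcome, is planned as a 3-month self-report, so the figure would cover responders only and no rule deals with the rest

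*Combined protocol and SAP*

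**What the plan says.** Section 4.4a makes adherence a primary outcome with two components. One is attendance at scheduled physiotherapy sessions. The other is "participant self-reported intervention adherence defined as the % of prescribed exercise sessions completed".

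The adherence row of the table in section 5.1a lists the second component as "Participant self-reported % of prescribed home exercise sessions completed". The table is broken in the text available, but the row has two measures and two time points. Read in order, attendance is taken at completion of the intervention and home exercise at 3 months after the first physiotherapy session.

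Attrition, which is part of the acceptability outcome in section 4.4a, counts "participants who fail to complete follow up data collection at 3 months".

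Section 4.3 contains two other possible sources of adherence data:
- "Participants will be provided with, and asked to complete, an exercise diary containing their exercises and guidance on achieving an effective dose".
- "At each review session participant adherence and achievement of short-term goals will be reviewed".

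Section 5.2a lists what is entered in the database: paper questionnaires, case report forms and treatment logs. Diaries are not on the list. The intervention-delivery items in sections 4.4b and 5.1a cover attendance and what was prescribed, not home sessions completed.

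For the denominator, section 4.3 asks for exercise "independently a minimum of three times per week on non-consecutive days". It adds that early on, when pain may limit intensity, "participants can perform their exercises more frequently if they find this beneficial". It also lets treatment end early by agreement once goals are met.

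Section 5.3a describes adherence with counts and percentages and states no analysis set. On missing data, section 5.3b says "Missing data for each questionnaire and item level missingness will be reported", with the aim of choosing instruments for future studies.

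**The concern.** The planned adherence measure and the definition of attrition depend on the same 3-month data collection. A participant who does not respond is counted in the attrition rate and drops out of the home-exercise figure. Followed as written, the plan yields a percentage among responders, and nothing tells the analyst to label it so or to show what the missing participants could do to it.

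This matters because the study exists to inform a larger trial. Section 3.2 deliberately sets no numerical targets, so the adherence percentage itself is what planners will carry forward. Section 3.1b also gives reason to take loss seriously: the one earlier trial comparing exercise programmes lost 52% of its participants, and the protocol reads this as a sign that parts of that design were not acceptable to them.

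The denominator is also open. The prescription is a weekly floor, the number of weeks varies with discharge, and the plan does not say how sessions beyond the prescription are treated.

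**Working it through.** **Plan's own figure.** The target of 15 (section 4.6a) is a pragmatic choice with no formula, and no expected adherence is stated. There is nothing to reproduce for this outcome.

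**Inputs.**
- N = 15 enrolled (section 4.6a).
- m = number without the 3-month report. Two scenarios: m = 3 (assumed), and m = 8, because 0.52 × 15 = 7.8 using the attrition cited in section 3.1b.
- R = mean adherence in responders, assumed to be 80%.
- L = mean adherence in those lost, unknown, so taken from 0% to 100%.

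**Effect of non-response.** Mean over all enrolled = [(15 − m) × R + m × L] / 15.

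| L | m = 3 | m = 8 |
|---|---|---|
| 0% | (12×80 + 3×0)/15 = 64.0% | (7×80 + 8×0)/15 = 37.3% |
| 40% | (960 + 120)/15 = 72.0% | (560 + 320)/15 = 58.7% |
| 80% | (960 + 240)/15 = 80.0% | (560 + 640)/15 = 80.0% |
| 100% | (960 + 300)/15 = 84.0% | (560 + 800)/15 = 90.7% |

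The responder figure differs from the all-enrolled mean by (m/15) × (R − L). Its sign is the sign of R − L, so the responder figure is too high only when those lost did less than responders. The width of the range is 100 × m/15, which is 20 points for m = 3 and 53.3 points for m = 8. That width does not depend on the assumed 80%.

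**Denominator.** If *prescribed sessions completed* is read strictly, the percentage cannot pass 100%. If early extra sessions were instead counted over the weekly floor of three, it could. Assuming 13 weeks, the denominator is 3 × 13 = 39. Five sessions a week for the first two weeks and three a week afterwards gives (2×5 + 11×3)/39 = 43/39 = 110%. The plan neither adopts nor excludes this reading, so it is a point to define and not a demonstrated error.

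**The case against.** The strongest reply is that the plan works to limit this gap. Section 5.1c provides at least one reminder, telephone or email contact for incomplete data, and completion in clinic when the last appointment falls within a week of 3 months. Section 5.1d has the lead investigator try to contact people who wish to withdraw or who do not adhere, to ask whether they will still give follow-up data. It also keeps data collected before withdrawal. Attrition and questionnaire return are reported in their own right, so a reader would see the response rate. The table names self-report as the mode without naming an instrument, and a diary is self-report too.

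Much of this stands. These steps shrink the gap, and the absence of any statement about diaries could be an omission of detail. But contact attempts do not close the gap, and keeping earlier data helps only if adherence was captured earlier, which the plan does not specify. A response rate printed nearby also does not show how far the missing participants could move the adherence figure.

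A reader might infer three stronger things that the documents do not support:
- **That the result is inflated.** The direction rests entirely on what those lost are assumed to have done. The protocol gives no data on this and says the reasons for the earlier trial's attrition are unknown.
- **That the measure is missing for exactly those lost to follow-up.** Diaries or session reviews could supply partial data if they were used, and someone who returns the other forms could leave this item blank.
- **That adherence will exceed 100%.** The stated definition, taken literally, stops at 100%. Extra sessions are allowed only initially, and exercising on non-consecutive days averages at most 3.5 sessions a week, or 3.5/3 = 117% even if extras were counted.

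**Conclusion.** The point holds in a limited form. As written, the home-exercise component would be a responders-only figure with no rule for participants who lack the 3-month report, although a source closer to the event is already in participants' hands. With 80% among responders, the all-enrolled mean is compatible with 64% to 84% if 3 of 15 are lost and with 37% to 91% if 8 are lost. These ranges rest on the assumed 80%, on the chosen numbers lost, and on adherence in those lost being anywhere from 0% to 100%. An upward error is plausible but not established.

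The scope is narrow. Session attendance does not depend on the 3-month report. No decision threshold is breached, because section 3.2 sets none. The consequence is for interpretation and for planning the next study, so this is a worthwhile, inexpensive improvement and not a flaw that undermines the trial.

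**What to change.** Amend sections 4.4a, 5.1a, 5.2a and 5.3 as follows:

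1. **Source.** Record diary entries on the case report form at each physiotherapy visit and make these the main source. Keep the 3-month self-report as back-up, and add diaries to the data-entry list.
2. **Denominator.** Define it for each participant as the sessions prescribed from the first physiotherapy session to agreed discharge or 3 months.
3. **Numerator.** Count only prescribed sessions as completed, so that the maximum is 100%, and report extra sessions separately.
4. **Reporting.** State the number with data out of all enrolled. Give the responders-only figure beside a sensitivity range for undocumented weeks. Zero should be the lower bound and not the main estimate, because a blank diary week is not proof that no exercise was done.

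The cost is a little data entry for about 15 diaries. The limits should be stated openly: diaries are still self-report, may be incomplete, and give nothing after a participant's last visit, so the sensitivity range is needed even with the better source. Nothing in the intervention or its delivery changes.
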